This will be a telephone call scheduled 10 days (+ 4 days) by a clinical research staff member to review blinded CGM data for the purpose of logging CGM parameters including average glucose with standard deviation, time in range, percent highs, percent lows, and severe lows, and days with CGM data. If the CGM is worn less than 60% of the time, the participant may be withdrawn from the study at the discretion of the study investigator. Each participant, with the help of a guardian, will insert a non-blinded sensor according to the Dexcom G6 user guide, connect the Dexcom to a compatible phone, and activate the share functions with the clinic. If the guardian is not able to set-up the Dexcom at home, the patient and guardian will be asked to come for Visit 2B within 5 days to have the non-blinded Dexcom set-up in clinic and assure that inserting the CGM is a skill that could be done independently. If the guardian or participant cannot demonstrate that they can set-up the CGM system independently, the participant will be withdrawn from the study.

Between Visit 2T and Visit 3, clinic research staff will actively monitor the participants' blood glucose levels remotely through an Apple iPad. Currently available commercial Dexcom software is able to monitor up to 10 devices on a single iPad, and we plan to have two iPads

throughout the study period. Active remote monitoring of CGM data will occur during 7 days per week between 8:00 AM and 8:00 PM.

The goal of the secure text messaging is to provide supervision and feedback to the adolescents that is supportive and collaborative, with the ultimate goals of increasing self-efficacy and improving diabetic self-management skills. The intention is not to make the texting platform cumbersome and to allow the participants freedom in making lifestyle choices that will not interfere with their diabetes control. Only reactive texts and coaching texts will be sent during the school hours.

Participants will still be able to use normal clinic communication methods through the electronic patient portal and diabetes telephone emergency line as usual. Participants will be free to optimize their treatment independently as previously educated about trend management. We will provide a letter for school indicating that the participants are a part of a study and they have to carry their cell phones with them and respond to text messaging from us.

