Reminder texts will also be sent to remind participants and guardians about upcoming research Visit appointments.

- Reinforcing. Texts will provide encouragement and reinforcement for adherence to diabetes related tasks. Examples will include texts stating “(screenshot image from the participant’s glucose trend), followed by “awesome control! Keep it up!”.
- Coaching. Texts in this category will include response to participants and guardians’ complaints and questions. They could include management of participant or guardian questions about abnormal blood glucoses or ketone management interventions. Clinic protocols to manage sick days will be utilized.

All Tigertext communication will be stored electronically in a secure shared file. It will be used to retrospectively calculate time invested by clinical staff, and analyze percentage of texting category used.

First Follow-up, Visit 3

This visit will be scheduled 11-12 weeks (+/- 5 days) after Visit 2B or visit 2T. Adverse events, insulin doses and concomitant medications will be reviewed by study staff. Height and weight will be measured, and a physical exam will be performed. A capillary blood sample will be obtained for HbA1c determination. CGM reports will be analyzed. Participants will complete the PHQ-9A, PEDS-QoL4, Collaborative Parent Involvement Scale, and SEDM.

If due to participant or family scheduling conflicts, the participant is unable to complete a clinic visit for Visit 3, then they can participate in a telemedicine visit. Participants will be requested to measure height and weight at home. A physical exam will be performed as fully able within the telemedicine platform. HbA1c will be obtained with other standard of care labs. CGM report analysis will not be affected by the telemedicine visit. Surveys for PHQ-9A, PEDS-QoL4, Collaborative Parent Involvement Scale, and SEDM will be sent via MyChart to the participant’s parent to be completed by the participant. Parents will send images of the completed surveys to the research team via MyChart.

We will discuss the next phase of the study during that visit. We will emphasize that the research staff will not monitor CGM data remotely, that research staff will not be real-time followers of their CGM data, and they will not be able to use TigerText to communicate with our clinic anymore. They will be encouraged to continue the activated alarms to allow for self-control.

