We will discuss that CGMs will continue to be made available to participants and guardians for diabetes care. Participants and guardians will still be able to communicate with our clinic through previously available means, mainly through the electronic participant portal and/or calling the urgent line, and they could ask the clinic staff to review past CGM readings to give clinical advice.

Second Follow-up, Visit 4/EOSV

This visit will be scheduled 11-12 weeks (+/- 5 days) after Visit 3. Adverse events, insulin doses and concomitant medications will be reviewed by study staff. Height and weight will be measured, and a physical exam will be performed. A capillary blood sample will be obtained for HbA1c. Participants will complete the PHQ-9A and PEDS-QoL4 surveys, Collaborative Parent Involvement Scale, and SEDM.

If due to participant or family scheduling conflicts, the participant is unable to complete a clinic visit for Visit 4, then they can participate in a telemedicine visit. Participants will be requested to measure height and weight at home. A physical exam will be performed as fully able within the telemedicine platform. HbA1c will be obtained with other standard of care labs. CGM report analysis will not be affected by the telemedicine visit. Surveys for PHQ-9A, PEDS-QoL4, Collaborative Parent Involvement Scale, and SEDM will be sent via MyChart to the participant's parent to be completed by the participant. Parents will send images of the completed surveys to the research team via MyChart.

This is the final study visit.

Evaluations

Medical History

- Age
- Gender
- Race/ethnicity
- Date of diagnosis of type 1 diabetes
- Hospitalizations and emergency department visits, particularly for diabetic ketoacidosis or hyperglycemia/ketosis/vomiting, or for severe hypoglycemia
- Surgeries
- Growth records for both height and weight
- Current doses of insulin
- Meal plan
- Other chronic medical conditions, particularly hypothyroidism or celiac disease
- Concomitant medications

Social history

- Family structure—one or two parent household, parents married or divorced, custody arrangements if divorced, genders and ages of siblings

- School details: name, grade, extracurricular activities, sports, schedule, school nurse information, and information about student insulin dosing during school hours if it is done through school nurse or independently by student.

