Collaborative Parent Involvement Scale		X		X	X

[figure not shown]

Figure 1. Timeline for study. Study visits are denoted by arrows. A timescale in months is below the timeline; there is not a specified interval between Visits 1 & 2.

Participant withdrawal criteria

The following study withdrawal criteria will apply:

1. Participants can terminate involvement in the study at any time point without any repercussions.
2. If data on the CGM is available < 60% of the time worn, patient may be withdrawn at the discretion of the research investigator.
3. If pregnancy occurs during study period.
4. Allergic reaction to adhesive surface of CGM sensor

Primary endpoint

The primary outcome is change in Hemoglobin A1c (HbA1c) between the baseline visit (Visit 2) and three-month follow-up visit (Visit 3) after active remote monitoring and secure text messaging.

A 5% significance level will be used to declare statistical significance for the primary outcome comparison.

Exploratory endpoints

- Change in Peds PHQ-9A, PED-QOL4A, SEDM, and Collaborative Parent Involvement Scale scores.
- Time taken for a text to be read by participant and guardian.
- Time spent by medical provider per participant per day.
- The difference in A1c between clinical remote monitoring HbA1c (Visit 3) and self-monitoring utilizing CGM (Visit 4)
- The difference in A1c from baseline (Visit 2) and after the two phases of the study intervention (Visit 4).
- The following outcomes will be compared between baseline, three months and six months using repeated measures ANOVA as follows:
 - Time spent in the target glucose range from 70–180 mg/dL
 - Time spent below target glucose 70 mg/dL

- Time spent above target glucose 180 mg/dL
- Average of time the participants wore the CGM

Statistical Plan

Paired sample t-tests will be used to assess continuous variable differences between two time points. Generalized linear models will be run to identify items in medical and social histories that could predict hemoglobin A1c, the primary outcome. Point estimates will be reported with 95% CIs.

As this is a pilot exploratory study, we will implement per-protocol analysis and not an intention-to-treat analysis. Only patients who have completed the three phases of the study will be included for analysis.

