Utilizing a standard deviation of HbA1c of 1.5%, a sample size of 18 participants will be required to detect a 1% change in HbA1c between the baseline measurement and 3-month measurement, assuming an alpha of 0.05 and a beta of 0.20 (80% power).

Safety endpoints

The following safety outcomes will be tabulated by treatment group:

- Number of subjects with any DKA events requiring hospitalization
- Number of subjects with any severe hypoglycemic or hyperglycemic events requiring an emergency room visit or hospitalization
- Number of episodes of moderate to large ketones managed in an outpatient basis

All adverse events will be listed for the entire study duration.

Data management

Dexcom Clarity reports will be used to obtain aggregate 90-day data regarding CGM parameters including average glucose with standard deviation, time in range, percent highs, percent lows, severe lows, and percent days with CGM data (this will be used to compare data across Visits 2T and Visit 4). Additionally, we will collect above data points retrospectively week-by-week for secondary analysis to evaluate progress over time.

Confidentiality of participant data will be observed during the study. Electronic data will be stored in secure password protected computers, and all paper records will be stored in locked researcher's offices. Anonymous data could be shared with third parties to advance diabetes treatment and for study publication purposes.

Protections Against Risk

Confidentiality

Privacy of Personal Data

The collection and processing of personal data from subjects enrolled in this study will be limited to those data that are necessary to fulfill the objectives of the study. These data will be collected and processed with adequate precautions to ensure confidentiality and compliance with applicable data privacy protection laws and regulations. Electronic data will be stored on secure servers that require password protection and maintain audit records of access, and/or on laptops with password-protected encrypted hard drives. All data sent between institutions via e-mail, file transfer protocols or physical media must be encrypted and password protected. Sponsor personnel whose responsibilities require access to personal data agree to keep the identity of study subjects confidential. Hardcopy documentation must be stored in locked file cabinets or locked offices secured with either key or badge access.

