The informed consent and HIPAA permission obtained from the subject's legally acceptable representative includes explicit consent for the processing of personal data and for the investigator to allow direct access to his or her original medical records for study-related monitoring, audit, IRB review, and regulatory inspection. This consent also addresses the transfer of the data to other entities and to other countries.

For any telemedicine visits completed, verbal consent to perform a telemedicine visit will be obtained from the participant's parent/legal guardian/legal representative. All telemedicine visits will be completed using Children's Health telemedicine platform.

The subject's legally acceptable representative has the right to request through the investigator access to the subject's personal data and the right to request rectification of any data that are not correct or complete. Reasonable steps will be taken to respond to such a request, taking into consideration the nature of the request, the conditions of the study, and the applicable laws and regulations.

Disclosure to outside entities

All data, whether electronic or hardcopy, will be referenced to a unique patient identifier, with subjects' identifying information kept in separate secure files. The following entities will be granted access to some or all data and specimens from this study:

- The UT Southwestern Institutional Review Board (IRB).
- Dexcom, Inc.
- Representatives of other governmental and regulatory agencies.

Data and Safety Monitoring Plan

This study represents minimal incremental risk over routine care for children with type 1 diabetes. Accordingly, a separate DSMB is not indicated.

ClinicalTrials.gov

We will register the study with ClinicalTrials.gov prior to enrolling any subjects.

Adverse event reporting

No investigational drug or device will be used in these studies, and consequently adverse event reporting, *per se*, is not applicable. However, we will monitor as secondary outcomes hypoglycemia frequency, DKA admission risk, and report all study adverse events.

Budget: \$37,300 (Dexcom, Inc will provide the CGM devices for the study)

Certified Diabetes Educator time - 36 hours per week \times 20 weeks of study \times \$50 per hour = \$36,000

iPad devices for monitoring CGM data – 2 devices \times \$350 per iPad _____ = \$700

Patient incentive gift cards – \$10 \times 3 visits \times 25 participants) _____ = \$600

[figure not shown]

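### Stopping the sensor is written as leaving the study, so a participant withdrawn before Visit 3 has no planned Visit 3 HbA1c and no scheduled adverse event review

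*Combined protocol and SAP*

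**What the plan says.** The Participant withdrawal criteria section opens with "The following study withdrawal criteria will apply" and has four items. Item 4 is "Allergic reaction to adhesive surface of CGM sensor", with no discretion attached. Item 2, low data capture, is left to the investigator's discretion, as it is in the methodology overview and under Visit 2B or 2T. The Visit 2B or 2T section adds a further route: if the family "cannot demonstrate that they can set-up the CGM system independently, the participant will be withdrawn from the study".

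HbA1c is planned at Visits 2, 3 and 4. The primary outcome is the change from Visit 2 to Visit 3. The Visit 3 and Visit 4 sections already accept an HbA1c drawn with standard-of-care labs when the visit is held by telemedicine.

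The only end-of-study visit is Visit 4, which is tied to the calendar and not to withdrawal: "This visit will be scheduled 11-12 weeks (+/- 5 days) after Visit 3".

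On safety, the Visit 3 and Visit 4 sections each state: "Adverse events, insulin doses and concomitant medications will be reviewed by study staff". No such step appears under Visit 2B or 2T. The Safety endpoints section promises: "All adverse events will be listed for the entire study duration". The Adverse event reporting section calls formal reporting inapplicable because nothing investigational is used, but still undertakes to "report all study adverse events".

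The Statistical Plan analyses only participants who finish all three phases.

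**The concern.** Being unable to use a sensor is a reason to stop the sensor. It does not prevent a fingerstick HbA1c three months later. By making it a reason to leave the study, the plan gives up the primary outcome in people who began the intervention and could not continue it. The effect can then be estimated only in those who tolerated the device. For a study whose title names both feasibility and effectiveness, the missing group is an informative one.

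This is a different problem from the completer-only analysis. An analysis set can be widened afterwards, but a value that nobody planned to collect cannot be relied on to exist.

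The same gap affects safety. Participants qualify through an annual DKA risk of at least 30% or an HbA1c of at least 12%, and DKA admission is a safety endpoint. A promise to list every event needs a step at which events are asked about, and early leavers have none on the schedule.

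**Working it through.** **Step 1. What is planned, by time of exit** (visit sections, assessment table, withdrawal criteria).

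| Exit | Sensor-related route | Visit 3 HbA1c | Scheduled adverse event review | Other staff contact |
|---|---|---|---|---|
| Visit 2 to 2T/2B (blinded run-in) | Failed set-up; low capture (discretionary); adhesive reaction | Not planned | None | Signal-loss notices; the 2T call or 2B visit |
| 2T/2B to Visit 3 (remote monitoring) | Adhesive reaction; low capture (discretionary) | Not planned | None | Monitoring 7 days a week, 8 AM to 8 PM; trend review about every 7 days; stored messages |
| Visit 3 to Visit 4 | Adhesive reaction; low capture (discretionary) | Already taken | Visit 3 only | Usual clinic channels |

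The collection gap for the primary endpoint lies in the first two rows. In the third row the value exists and is set aside only by the completer rule.

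**Step 2. Reproduce the plan's sample size.** Inputs from the Statistical Plan: SD 1.5%, change 1%, alpha 0.05, power 80%, paired t-test. The plan does not say whether 1.5% is the SD of the change or whether the test is two-sided; both are assumed here.

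n = [1.5 × (1.960 + 0.842) / 1]² = 17.66, rounded up to 18. The plan's figure is reproduced. An exact paired t calculation gives 20 (power 80.7%), and at 18 its power is 76.0%.

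**Step 3. Room for losses.** Enrolment is 25. 25 − 18 = 7, and 7/25 = 28%. Against the exact figure, 25 − 20 = 5, and 5/25 = 20%. This is the margin between two planning numbers, not a forecast. The documents give no rate of adhesive reaction, failed set-up or withdrawal.

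**Step 4. Illustration of what non-collection could hide (assumed values).** Suppose all 25 start remote monitoring, 18 stay and fall by 1.0%, and 7 leave before Visit 3 with a mean change x. The mean over all starters is (18 × −1.0 + 7x)/25.

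| x | Mean over 25 |
|---|---|
| −1.5 | −28.5/25 = −1.14 |
| −1.0 | −25/25 = −1.00 |
| 0 | −18/25 = −0.72 |
| +0.5 | −14.5/25 = −0.58 |
| +1.0 | −11/25 = −0.44 |

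With x = 0 and fewer leavers, the mean is −(25 − k)/25: −0.96 for k = 1, −0.88 for k = 3 and −0.80 for k = 5. Completers would show −1.0% in every case. The direction as well as the size depends on x, which the plan as written would not observe.

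**Step 5. Adverse events.** Three commitments stand: a listing for the whole study, reporting of all study events, and treating clinically significant physical findings as adverse events. Against them, review is scheduled at Visits 3 and 4, and physical examinations at Visits 2, 3 and 4. For someone who leaves before Visit 3, no scheduled step after baseline serves those commitments.

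**The case against.** A reader might infer that the event that caused removal is never collected, or that safety ascertainment before Visit 3 is nil. The documents do not support either. Staff must know of an adhesive reaction to apply item 4, the commitments in Step 5 cover it, and from Visit 2T there is daily monitoring and roughly weekly contact with stored messages. The supportable gap is a missing capture step. It is not a contradiction of the listing commitment, and it is most exposed in the short run-in.

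A reader might also infer that HbA1c is lost for everyone withdrawn. It is not: baseline is always taken, and those leaving after Visit 3 have the primary value.

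Three further objections carry weight:

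- **The routes differ.** Low capture is discretionary, so staying in is already allowed. Failed set-up occurs before remote monitoring, in a phase declared as a run-in, and a later HbA1c from those participants would describe usual care. This stands, and the HbA1c remedy is limited to those who started remote monitoring. Known adhesive allergy is also an exclusion, which should make item 4 less common.
- **Seven is not a withdrawal rate.** This stands. Losses would also include voluntary exit and pregnancy, which are not sensor problems. The assumed changes have no source in the documents, and improvement among leavers is possible because many may enter at a high HbA1c.
- **The extra values would enter no planned analysis.** This stands too. The completer rule is an open choice for a pilot, so collecting the values is useful only if they are also reported.

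**Conclusion.** The point holds in this limited form. Sensor discontinuation is tied to study withdrawal, no exit assessment or off-device HbA1c follow-up is planned, and adverse event review is not scheduled before Visit 3. The consequence falls on participants withdrawn before Visit 3. The HbA1c part matters most for those who had begun remote monitoring; the adverse event part applies to all of them.

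The size is unknown. The −0.72, −0.58 and −0.44% figures rest on an assumed seven leavers, an assumed 1.0% fall in stayers and assumed changes in leavers, and show only that the effect could be material. A reader should not take 28% as an expected loss or −0.44% as an expected result. The change is worth making because it is cheap and because data not collected at the time may not be recoverable.

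**What to change.** 1. In the Visit 2B or 2T and Participant withdrawal criteria sections, separate stopping CGM and remote monitoring from withdrawing from the study. The criteria for stopping the sensor stay as they are.
2. For participants who started remote monitoring, stop before Visit 3 and do not withdraw consent, obtain HbA1c at the planned Visit 3 date, from a clinic or standard-of-care sample.
3. In the Statistical Plan, keep the completer analysis and add a supportive one: the Visit 2 to Visit 3 change, with its 95% CI, in all who started remote monitoring, stating how many lack a Visit 3 value. This also uses the values of those who leave after Visit 3.
4. Add an adverse event review at Visit 2T/2B and at the contact where any participant is withdrawn.

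The cost is amendment wording, a few HbA1c values at a time point that already exists, and a few questions, mostly at existing contacts. Some participants who stop will still decline follow-up, so the gap will narrow but not close.

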Schedule of procedures

Screening, Visit 1

Screening visit. It will include review of inclusion and exclusion criteria and obtaining informed consent from legal guardians and assent from participants. The visit is expected to take around one hour. The visit can be combined with Visit 2.

Participants will be recruited from either an endocrinology inpatient floor or the outpatient clinic.

Baseline, Visit 2

The visit will include review of diabetes history including current doses, prior hospitalizations, previous complications, and detailed medical and social histories and a complete physical examination that will include measurement of height and weight. A capillary blood sample will be obtained for HbA1c determination using the Alere Afinion device. A HbA1c from within two weeks of Visit 2 may also be used. A urine pregnancy test will be performed on females capable of becoming pregnant.

Participants and guardians will be introduced to the concept of a continuous glucose monitor in general, with specific details about how to apply, use, and share the Dexcom G6 data. Mandatory alarms will be set for participants and followers for blood glucose below 70 mg/dL, blood glucoses above 250 mg/dL, “urgent low soon”, “signal loss”, and “no reading” alerts. Participants may set extra alarms to personalize their diabetes alerts. Participants will also be taught to log their food and insulin intake into the CGM device.

Participants will complete the PHQ-9A, PEDS-QoL4, Self-Efficacy for Diabetes Self-Management measure (SEDM) questionnaire, and Collaborative Parent Involvement Scale. A blinded CGM will be placed on the participant with the goal to obtain baseline data for 10 days. A test secure text message will be sent through TigerConnect to guardian and participant, and they will be introduced to the messaging platform used. We will determine with the participants and parents their preferred contact hours and school hours to allow texting for non-urgent matters to be done at convenient times. This visit will take up to 2 hours.

Between Visit 2 and Visit 2T, participants and clinical staff will be notified if there is signal loss from the blinded CGM. Dexcom, Inc. will provide troubleshooting of the blinded CGM if any technical issues arise. Participants will be asked to continue taking care of their diabetes as usual and will not have access to the CGM data.

Telephone or Clinic Follow-up, Visit 2B or 2T

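### For the exploratory CGM outcomes, the completer-only rule together with repeated measures ANOVA discards usable baseline and month-3 data and can bias the within-person change; sphericity is a lesser matter

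*Combined protocol and SAP*

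**What the plan says.** Under Exploratory endpoints, four CGM outcomes (time in range, below range, above range, and wear) are handled in one sentence: "The following outcomes will be compared between baseline, three months and six months using repeated measures ANOVA as follows". No sphericity correction, covariance structure or missing-data rule is given.

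The Statistical Plan sets the analysis population: "we will implement per-protocol analysis and not an intention-to-treat analysis", and "Only patients who have completed the three phases of the study will be included for analysis". It assigns paired t-tests to differences between two time points.

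The CGM windows differ in length. Under Baseline, Visit 2, the aim of the blinded sensor is to "obtain baseline data for 10 days". Under Data management, the Clarity reports supply "aggregate 90-day data regarding CGM parameters". Visits 3 and 4 each fall 11-12 weeks (± 5 days) after the previous stage. Week-by-week CGM values are also collected.

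The design has 25 participants and no control group. Participants may leave at any time, and the investigator may withdraw those with low CGM data.

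**The concern.** A participant who wears the sensor through the run-in and the monitored phase, then leaves during phase 3, has everything needed for the baseline to month-3 change. Under this plan that participant contributes nothing to it. Two provisions produce the loss: the completer rule removes the person from the analysis set, and standard repeated measures ANOVA would drop anyone lacking one of the three periods in any case.

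If those who leave gained less than those who stay, the completers' mean change is too high at both later times; if they gained more, it is too low. With no control arm, that bias passes straight into the reported effect and into any later trial planned from this pilot.

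A second, smaller worry is that ANOVA assumes equal variances for all pairwise differences. A 10-day mean is noisier than one over 11-12 weeks, so differences involving baseline may be more variable than the month-3 to month-6 difference.

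**Working it through.** **The plan's own figure.** The only sample size given is for HbA1c. With SD 1.5 (read as the SD of the change), difference 1, two-sided alpha 0.05 and 80% power: n = [(1.960 + 0.842) × 1.5/1]² = 17.66, rounded up to 18. This reproduces the stated 18. Enrolling 25 leaves room to lose 7 (7/25 = 28%). That is not a dropout forecast, and the plan gives none. No figure is given for the CGM outcomes, so all CGM inputs below are assumptions.

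**Effect of selective loss.** Assumed: 25 participants; SD of time in range 17.1, 15 and 15 points at baseline, month 3 and month 6; correlations 0.6 (baseline, month 3), 0.5 (baseline, month 6) and 0.7 (month 3, month 6); true gains +8 and +6; about 30% lost before Visit 4. Retention is logistic in the observed month-3 gain. Mean estimates over simulated trials (simulation error about 0.1):

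| Log-odds of staying, per point of gain | Completers, month 3 / month 6 |
|---|---|
| 0 (unrelated) | +8.0 / +6.1 |
| 0.02 | +9.2 / +6.9 |
| 0.04 | +10.4 / +7.9 |
| 0.06 | +11.3 / +8.6 |
| 0.10 | +12.6 / +9.8 |

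Maximum likelihood on all available data stays within about 0.2 points of +8/+6 in every row.

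The last row is strong selection: retention is about 43% at one SD below the mean gain and 93% at one SD above. For scale, the SD of the month-3 gain is √(17.1² + 15² − 2 × 0.6 × 17.1 × 15) = 14.5. Losing exactly the worst 30% would shift the mean by at most 7.2 points, so a shift of 4.6 is 64% of the maximum.

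**Precision.** Assume a day-to-day SD of 15 points and a person-by-period SD of 5, with covariance treated as known. The variance of one person's baseline to month-3 change is (25 + 225/10) + (25 + 225/90) = 75.

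- 18 completers: SE = √(75/18) = 2.04.
- 7 more with both baseline and month 3: SE = √(75/25) = 1.73.
- 7 more with baseline only: SE 2.00, almost no gain.

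**Does changing the model alone help?** On one simulated complete set (18 people, 54 observations), a random-intercept mixed model gave F = 17.67 and repeated measures ANOVA gave F = 17.67. With completers only, that model recovers nobody and keeps the same covariance assumption.

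**Sphericity.** Assumed: windows of 10/90/90 days, between-person SD 12, day-to-day SD 10, 15 or 20, n = 18 or 25, nominal level 0.05.

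| Person-by-period SD | Greenhouse-Geisser epsilon | Uncorrected omnibus type I error |
|---|---|---|
| 0 | 0.65 | 0.069-0.074 |
| 5 | 0.92-0.99 | 0.049-0.054 |
| 10 | 0.99-1.00 | 0.050-0.054 |

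With 60% wear (6/54/54 days, day-to-day SD 15, person-by-period SD 5, n = 18), epsilon is 0.93 and the error 0.056. With the covariance used in the dropout simulation, epsilon is 0.88 and the error about 0.057. An unstructured-covariance test holds 0.048-0.053, and a Greenhouse-Geisser correction gives 0.045-0.051.

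Contrasts using the pooled ANOVA error fare worse. For baseline against month 3, the null rejection rate is 0.09-0.10 at person-by-period SD 0 and 0.055-0.066 at SD 5. For month 3 against month 6 it is 0.001 and 0.022-0.043. Ordinary paired t-tests stay near 0.05.

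**The case against.** The strongest reply is that the ANOVA is not what removes dropouts. The completer rule acts first, and the ANOVA by itself would drop only a completer without usable CGM data in one period. The plan also uses paired t-tests for two-point comparisons, so a phase-3 dropout could stay in a baseline to month-3 test if the rule were absent. This stands. A reader might infer that a mixed model fitted to the same completers would solve the problem; it would not, because the analysis set has to change too. Equally, lifting the rule while keeping the three-period ANOVA would still drop these people from that analysis.

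A reader might also infer that the unequal windows make the F test invalid. The documents do not support that. They give no CGM variances, and across the assumed range the omnibus error rises by at most about 2 percentage points. A Greenhouse-Geisser correction would handle it, and the plan does not say that pairwise contrasts will use the pooled error.

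Nor do the documents show that completer results will be inflated by more than half. The +12.6 figure needs strong selection, and unrelated dropout gives no bias.

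Finally, likelihood estimation looks good in the simulation because dropout there depends on observed data. Withdrawal linked to low CGM wear may not behave so, least of all for wear itself. This stands as a limit on the remedy. The outcomes are exploratory, and the 5% level is declared only for HbA1c, which limits the consequence.

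**Conclusion.** The concern holds in a limited form. For the CGM outcomes, the completer rule and the three-period ANOVA together discard valid baseline and month-3 data. In an uncontrolled study this can bias the within-person change by anything from nothing to about 4.6 points at month 3 (12.6 − 8) and 3.8 at month 6 (9.8 − 6), given about 30% loss and the assumed covariance. The size depends on how closely dropout follows gain, which the documents cannot tell us. Sphericity is secondary: the direction of the departure is clear, and its likely effect on the omnibus test is small. The change is worth making because it is cheap and these are the main CGM results, but it does not affect the primary HbA1c test.

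**What to change.** In the SAP, for the four CGM outcomes only:

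- Lift the completer-only restriction. Include every participant with at least one valid CGM period, and define what counts as valid.
- Replace repeated measures ANOVA with a linear mixed model: visit as a fixed effect, unstructured covariance, REML, Kenward-Roger degrees of freedom. A random intercept alone is not enough.
- Report the month-3 and month-6 contrasts against baseline with 95% CIs.
- Keep the completer analysis as a sensitivity analysis, and tabulate the number contributing at each period with reasons for loss.

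The cost is SAP wording and a standard procedure; no new data are needed. There are two downsides. The CGM analysis departs from the stated per-protocol set and relies on missing at random, which should be acknowledged as doubtful where withdrawal follows low wear.

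The model also does not repair the CGM windows. Phases of 72-89 days (77 − 5 to 84 + 5) are shorter than a 90-day report, so a Visit 4 look-back would reach 1-18 days into the monitored phase, and only about 10 days exist at Visit 2T. Each window should be aligned to its phase separately; the weekly values already being collected should allow this.
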